8.3.3 Appropriateness of efficacy assessments

UAS7: The UAS7 score is a unified, simple, well-established and validated tool, recommended by the current urticaria guidelines for the assessment of disease activity and treatment response in real-world clinical practice as well as in clinical trials with urticaria patients (Mlynek et al 2008, Hawro et al 2018, Zuberbier et al 2018). It is based on the assessment of the two key urticaria signs and symptoms, wheals and pruritus, which are documented by the patient, making this score especially valuable. The use of the UAS7 facilitates comparison of study results across different trials, since it is used in other major Phase 3 trials in the CSU indication as well (e.g., with ligelizumab).

[figure not shown]
AAS7: The AAS7 score is a unified, simple and validated tool, recommended by the current urticaria guidelines for the assessment of disease activity and treatment response in patients with angioedema (Weller et al 2013, Zuberbier et al 2018). The use of the AAS7 facilitates comparison of study results across different trials, since it is used in other major Phase 3 trials in the CSU indication as well (e.g., with ligelizumab).

[REDACTED]

8.3.4 Other assessments: evidence of urticaria

[figure not shown]
The investigator must confirm the presence of urticaria (i.e., the presence of hives) in each participant before randomization by direct physical examination. In the absence of active disease at the screening and/or randomization visit, the following will be acceptable: (a) a clearly identifiable photograph of the participant that is no older than 3 months showing the presence of urticaria, (b) the investigator must have seen the participant with active CSU in the past 3 months, or (c) the presence of hives/wheals must have been documented in the medical record of the participant by a physician trained in the management of urticaria in the past 3 months.

[REDACTED]

8.4 Safety

Safety assessments are specified below with the assessment schedule detailing when each assessment is to be performed.

[figure not shown]

For details on AE collection and reporting, refer to AE section.

As per [Section 4.6](#), during a Public Health emergency as declared by Local or Regional authorities i.e., pandemic, epidemic or natural disaster, that limits or prevents on-site study visits, regular phone or virtual calls can occur (every 4 weeks or more frequently if needed) for safety monitoring and discussion of the participant's health status until it is safe for the participant to visit the site again.

Table 8-8 Physical assessments

Assessment	Specification
Physical examination	
A complete physical examination (performed at Screening) will include the examination of general appearance, skin, neck (including thyroid), eyes, ears, nose, throat, lungs, heart, abdomen, back, lymph nodes, extremities, vascular, neurological and body temperature measurement (per local practice). If indicated based on medical history and/or symptoms, rectal, external genitalia, breast, and pelvic exams will be performed.
 
A short physical exam (performed at all visits except Screening) will include the examination of general appearance, assessment of the skin for signs of urticaria and other skin lesions, body temperature measurement (per local practice) and vital signs (blood pressure (BP) [systolic blood pressure (SBP) and diastolic blood pressure (DBP)] and pulse).
 
Information for all physical examinations must be included in the source documentation at the study site. Clinically relevant findings that are present prior to signing informed consent must be recorded on the appropriate CRF that captures medical history. Significant findings made after signing informed consent which meet the definition of an Adverse Event must be recorded as an adverse event.

Vital signs	
Vital signs include BP and pulse measurements. After the participant has been sitting for five minutes, with back supported and both feet placed on the floor, systolic and diastolic blood pressure will be measured three times using an automated validated device, e.g., OMRON, with an appropriately sized cuff. The repeat sitting measurements will be made at 1 - 2 minute intervals and the mean of the three measurements will be used. In case the cuff sizes available are not large enough for the participant's arm circumference, a sphygmomanometer with an appropriately sized cuff may be used.

Assessment	Specification
	Clinically notable vital signs are defined in Section 16.1 .
Height and weight	Height in centimeters (cm) and body weight (to the nearest 0.1 kilogram (kg) in indoor clothing, but without shoes) will be measured as specified in Table 8-1 .

8.4.1 Laboratory evaluations

A central laboratory will be used for analysis of all specimens detailed in this section ([Table 8-9](#)) unless noted otherwise. Details on the collections, shipment of samples and reporting of results by the central laboratory are provided to investigators in the laboratory manual.

[figure not shown]
If participants cannot visit the site for protocol specified safety lab assessments (per [Section 4.6](#)), an alternative lab (local) collection may be used.

Clinically notable laboratory findings are defined in [Section 16.1](#).

Clinically significant abnormalities must be recorded on the relevant section of the eCRF capturing medical history/current medical conditions/AEs.

Table 8-9 Laboratory assessments

Test Category	Test Name
Hematology	Hematocrit, Hemoglobin, [in the case of clinically significant anemia the following parameters will be assessed: Ery. Mean Corpuscular Hemoglobin (MCH), Ery. Mean Corpuscular Hemoglobin Concentration (MCHC), Ery. Mean Corpuscular Volume (MCV)], Platelets, Erythrocytes, Leukocytes, and Differential (Basophils, Eosinophils, Lymphocytes, Monocytes, Neutrophils, Bands)
Chemistry	Albumin, Alkaline phosphatase (ALP), Alanine Aminotransferase (ALT), Aspartate Aminotransferase (AST), Gamma-glutamyl transferase (GGT), Lactate dehydrogenase (LDH), Calcium, Magnesium, Phosphate, Chloride, Sodium, Potassium, Creatinine, Creatine Kinase (CK), Direct Bilirubin, Indirect Bilirubin (in case of clinically significant elevation), Total Bilirubin, Total Cholesterol, Low Density Lipoprotein (LDL) Cholesterol, High-Density Lipoprotein (HDL) Cholesterol, Total Protein, Triglycerides, Urea Nitrogen or Urea, Uric Acid, Amylase, Lipase. C-reactive protein (CRP), estimated Glomerular Filtration Rate (eGFR): in all patients at screening, baseline, weeks 12, 24 and 52 and when deemed necessary by the investigator at later visits.

Test Category	Test Name
	Fasting glucose assessed at randomization, weeks 2, 12 and 52.
Urinalysis	Done on site (unless prohibited by local guidelines, then sample to be sent to central laboratory) Macroscopic Panel (Dipstick) (Color, Bilirubin, Occult Blood, Macroscopic Blood, Glucose, Ketones, Leukocytes esterase, Nitrite, pH, Protein, Specific Gravity, Urobilinogen)
Coagulation	Prothrombin time (PT), International normalized ratio (INR), Activated partial thromboplastin time (APTT)
Hepatitis screening	Hepatitis B screening: Antibodies against Hepatitis B virus core antigen (HBcAb or anti-HBc); antibodies against Hepatitis B virus surface antigen (anti-HBs or HBs-Ab); Hepatitis B virus surface antigen (HBsAg) Hepatitis B-Deoxyribonucleic acid (HBV-DNA), only in participants who are positive for anti-Hepatitis B virus Core (HBcAb or anti-HBc). Hepatitis C screening: Hepatitis C virus antibodies (anti-HCVAb) and Hepatitis C-Ribonucleic acid (HCV-RNA, only in participants who are positive for anti-HCVAb)
Hepatitis B re-activation monitoring	Only in participants who are positive for HBc-Ab (anti-HBc positive) and negative for anti-HBsAg and HBV-DNA at screening: HBsAg, HBV- DNA
HIV testing	HIV test performed at screening, only when required by local regulations.
Additional tests	 Follicle-stimulating hormone (FSH) (for female participants with unclear fertility status)
Pregnancy Test	Serum / Urine pregnancy test for WoCBP (refer to 'Pregnancy and assessments of fertility' Section 8.4.3)

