GGT	Gamma-glutamyl transferase
GLDH	Glutamate dehydrogenase
h	Hour
HBc	Hepatitis B core
HBcAb	Antibodies against hepatitis B core antigen (anti-HBcAg antibodies)
HBsAb	Antibodies against hepatitis B surface antigen (anti-HBsAg antibodies)
HBsAg	Hepatitis B virus surface antigen
HBV	Hepatitis B Virus
HCP	Healthcare Professional
HCV	Hepatitis C Virus
HCVAb	Hepatitis C Virus Antibody
HDL	High-Density Lipoprotein
hERG	Human ether-a-go-go related gene
HIV	Human Immunodeficiency Virus
HRQoL	Health-Related Quality of Life
HSS	Hives Severity Score
HSS7	Weekly Hives Severity Score
i.v.	Intravenous
IA	Intra-articular
IB	Investigator's Brochure
ICF	Informed Consent Form
ICH	International Council for Harmonization of Technical Requirements for Pharmaceuticals for Human Use
IEC	Independent Ethics Committee
Ig	Immunoglobulin
IMP	Investigational Medicinal Product
IN	Investigator Notification
INR	International Normalized Ratio
IRB	Institutional Review Board
IRT	Interactive Response Technology
ISS	Itch Severity Score
ISS7	Weekly Itch Severity Score
■	■
■	■
J2R	Jump to Reference
KDIGO	Kidney Disease Improving Global Outcome

LC-MS/MS	Liquid Chromatography-Mass Spectrometry
LDH	Lactate Dehydrogenase
LDL	Low-Density Lipoprotein
LFT	Liver Function Test
LLOQ	Lower Limit of Quantification
LTRA	Leukotriene Receptor Antagonists
MAR	Missing At Random
MCH	Mean Corpuscular Hemoglobin
MCHC	Mean Corpuscular Hemoglobin Concentration
MCV	Mean Corpuscular Volume
MedDRA	Medical Dictionary for Regulatory Activities
mg	Milligram(s)
MI	Multiple Imputation
ml	Milliliter(s)
MMRM	Mixed effect Model for Repeated Measures
NOAC	Novel Oral Anti Coagulant
NSAID	Nonsteroidal Anti-Inflammatory Drug
PA	Primary analysis
Pbo	Placebo
PCR	Protein-creatinine ratio
PD	Pharmacodynamic(s)
PE	Primary endpoint
█	█
█	█
PK	Pharmacokinetic(s)
PRO	Patient Reported Outcomes
PT	Prothrombin Time
q.d.	Once a Day
QMS	Quality Management System
QTcF	QT interval corrected by Fridericia's formula
RAS	Randomized Set
RDO	Retrieved Drop Out
RNA	Ribonucleic Acid
s.c.	Subcutaneous
SAE	Serious Adverse Event
SAF	Safety Set
SBP	Systolic Blood Pressure
SD	Standard Deviation
SjS	Sjogren's Syndrome
SMQ	Standardized MedDRA Query
SUSAR	Suspected Unexpected Serious Adverse Reaction

TBL	Total Bilirubin
█	█
UAS	Urticaria Activity Score
UAS7	Weekly Urticaria Activity Score
█	█
ULN	Upper Limit of Normal
UPDD	Urticaria Patient Daily Diary
UV	Ultraviolet
WHO	World Health Organization
WoCBP	Women of Child Bearing Potential
█	█

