 23. Evidence of an ongoing Hepatitis C infection (e.g., defined by the detection of hepatitis C virus ribonucleic acid (HCV-RNA) at screening) and/or an ongoing Hepatitis B infection (defined by the detection of hepatitis B virus surface antigen (HBsAg) and/or hepatitis B virus (HBV)-DNA at screening; participants who are positive for anti-hepatitis B core (HBc) antibodies but who are negative for antibodies against HBsAg and HBV-DNA can be included into the study if they agree to monitoring for HBsAg and HBV-DNA re-activation)
 24. Known or suspected ongoing, chronic or recurrent infectious disease including but not limited to opportunistic infections (e.g., tuberculosis, atypical mycobacterioses, listeriosis or aspergillosis) and/or known positivity for Human Immunodeficiency Virus (HIV) infection. HIV antigen/antibody tests will be performed to determine HIV status if required according to local regulations.

6 Treatment

[figure not shown]

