² Serum pregnancy test and fertility assessment will be done at Screening. Urine pregnancy test to be completed every 4 weeks by WoCBP from Randomization through Study completion visit. At Weeks 28, 36, 44 and 48 test may be performed at home - sites must contact participants to obtain test results. Any positive or undetermined test result must be confirmed by a serum pregnancy test done by central lab and results obtained electronically. Urine pregnancy results are reported as source. If participants are not able to perform a home urine pregnancy test (e.g., prohibited by local regulations), a urine or serum test can be performed at the local laboratory.

³ Participants eDiary will be returned to site at either week 52/study discontinuation.

⁴ Complete physical exam at screening, short physical exam at all subsequent visits including body temperature monitoring (per local practice)

⁵ Height collected at screening visit only

⁶ pre and post dose

⁷ eDiary includes UPDD (Urticaria Patient Daily Diary) with UAS (Urticaria Activity Score, part of UPDD) and AAS (Angioedema Activity Score), eDiary to be completed from screening to week 52/study discontinuation

⁸ Completed in the patient's eDiary during site visit. Order of completion: DLQI [REDACTED]. All questionnaires should be completed prior to any other physician assessment.

[REDACTED]

¹⁴ Hepatitis B re-activation monitoring only for participants who were HBsAg negative and HBcAb (anti-HBc) positive with a negative HBV DNA test at Screening.

[figure not shown]
[REDACTED]

[REDACTED]

Period	Screening	Treatment											Follow-up	Unscheduled visit	
Visit Name	Screening	Baseline/ Randomization ¹	week 2 ¹	week 4	week 8	week 12 ¹	week 16	week 20	week 24	week 32	week 40	Early treatment discontinuation	week 52/Study discontinuation ¹	week 56/Safety FU/Study completion	Unscheduled visit
Days	-28 to -1	1	15	29	57	85	113	141	169	225	281		365	394	-

¹⁶Dispensation for background medication covers prescription, dispensation and/or instruction of the participant on dosing and use of background medication and protocol requirements, considering different procedures for the provision of background medication at investigational sites. At Week 56/Safety FU/Study completion visit only compliance to be checked

¹⁷ Only for participants who have completed Week 52 visit, not applicable at Study discontinuation visit

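### Hepatitis B re-activation monitoring is defined by the surface antibody in Table 8-9 and criterion 23 but by the surface antigen in Table 8-1 footnote 14, so one participant profile is monitored under one rule and not the other

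*Protocol*

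**What the plan says.** Three places in the protocol describe the core-antibody-positive participants who enter with, or receive, re-activation monitoring.

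- **Section 5.2, exclusion criterion 23.** Ongoing hepatitis B is "defined by the detection of hepatitis B virus surface antigen (HBsAg) and/or hepatitis B virus (HBV)-DNA at screening". A parenthesis then adds that anti-HBc-positive people who are "negative for antibodies against HBsAg and HBV-DNA can be included into the study if they agree to monitoring for HBsAg and HBV-DNA re-activation".
- **Section 8.4.1, Table 8-9, re-activation row.** Monitoring is limited to those who are anti-HBc positive and "negative for anti-HBsAg and HBV-DNA at screening".
- **Table 8-1, footnote 14.** "Hepatitis B re-activation monitoring only for participants who were HBsAg negative and HBcAb (anti-HBc) positive with a negative HBV DNA test at Screening".

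Two further places fix the vocabulary. The list of abbreviations expands HBsAb as "Antibodies against hepatitis B surface antigen (anti-HBsAg antibodies", with a separate entry for HBsAg as the antigen. The hepatitis screening row of Table 8-9 lists the two as distinct assays: "antibodies against Hepatitis B virus surface antigen (anti-HBs or HBs-Ab); Hepatitis B virus surface antigen (HBsAg".

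Section 6.6 defines re-activation as newly detectable HBV-DNA or a positive HBsAg, and sets out antiviral treatment and interruption of study drug when it occurs.

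**The concern.** Criterion 23 and Table 8-9 refer to the antibody against the surface antigen; footnote 14 refers to the antigen itself. By the protocol's own abbreviations these are different markers, and a participant can be positive for one and negative for the other. Table 8-9 and footnote 14 each carry a limiting *only*, so each shuts out anyone outside its own definition. They cannot be read as complementary.

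At stake is who has HBsAg and HBV-DNA measured during treatment. The actions in Section 6.6 are triggered by those two results, and a participant who is not tested cannot produce them. If one site or laboratory works from Table 8-9 and another from footnote 14, they could test different people, and re-activation could be missed in some participants taking a drug whose immunomodulatory effects Section 4.5 describes. Criterion 23 also makes entry conditional on agreeing to monitoring, so the group asked to agree depends on the same wording.

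**Working it through.** No power, alpha or sample size calculation is involved. The check lists every combination of the three markers in an anti-HBc-positive participant (2 × 2 × 2 = 8) and applies each rule literally.

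- **Excluded as ongoing infection (criterion 23):** HBsAg positive or HBV-DNA positive.
- **Antibody rule (Table 8-9, and the wording of criterion 23's parenthesis):** anti-HBs negative and HBV-DNA negative.
- **Antigen rule (footnote 14):** HBsAg negative and HBV-DNA negative.

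| anti-HBs | HBsAg | HBV-DNA | Excluded as ongoing infection | Antibody rule | Antigen rule | Rules agree? |
|---|---|---|---|---|---|---|
| − | − | − | no | monitor | monitor | yes |
| − | − | + | yes | no | no | yes |
| − | + | − | yes | monitor | no | **no** |
| − | + | + | yes | no | no | yes |
| + | − | − | no | no | monitor | **no** |
| + | − | + | yes | no | no | yes |
| + | + | − | yes | no | no | yes |
| + | + | + | yes | no | no | yes |

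The rules differ in two of the eight rows.

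1. **anti-HBs −, HBsAg +, HBV-DNA −.** This falls inside the literal Table 8-9 rule and outside footnote 14. The participant is already excluded because HBsAg is detected, so the difference has no practical effect.
2. **anti-HBs +, HBsAg −, HBV-DNA −.** This does not meet the definition of ongoing infection. Footnote 14 includes the participant; Table 8-9 does not. Criterion 23's permissive parenthesis does not name this profile either.

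The conflict that matters is therefore one profile, and it runs in one direction.

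On frequency, Table 8-1 marks re-activation monitoring at Weeks 4, 8, 12, 16, 20, 24, 32, 40 and 52, which is nine scheduled treatment visits, plus early treatment discontinuation, Week 56 and unscheduled visits. A participant with this profile is due all of these under footnote 14 and none under Table 8-9.

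**The case against.** **The antibody wording may be a slip of terminology.** Criterion 23 defines infection by HBsAg and HBV-DNA, the tests listed for monitoring are those two, and Section 6.6 defines re-activation by them. That context may make divergent practice less likely. But the antibody wording appears twice, and in criterion 23 it is spelled out in words. Someone working from Table 8-9 has no textual ground to override it.

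**Criterion 23 may keep the affected profile out of the trial.** If its parenthesis is the only way in for anti-HBc-positive people, nobody with this profile is enrolled and nobody goes unmonitored. This reading is possible, although the criterion's own definition of ongoing infection does not exclude them. It does not remove the conflict; it moves it to eligibility, because footnote 14 would then provide monitoring for people who should not have been randomized. Criterion 23 is strictly an eligibility rule, so the direct clash over monitoring is between Table 8-9 and footnote 14.

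**Practice may already be settled.** Section 8 names Table 8-1 as the schedule of all assessments, and the laboratory manual may resolve the point. The manual is not among the documents, so what the laboratory does is unknown. This is why the harm is stated as possible, not as fact.

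**There is a backstop.** Clinical chemistry, including ALT and AST, is scheduled for everyone at every visit, with liver triggers in Appendix 2. Section 6.6 also applies to re-activation however it is found. Both points stand, but transaminases do not supply the HBsAg or HBV-DNA result that defines the event.

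**Conclusion.** The inconsistency is real and sits in current, unredacted text. It affects every participant who is anti-HBc positive, anti-HBs positive, HBsAg negative and HBV-DNA negative: monitored under footnote 14, not monitored under Table 8-9, and of unclear eligibility under criterion 23. The textual conflict is certain. Missed testing is conditional: it requires that such participants are enrolled and that Table 8-9 is the passage followed.

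The documents give no prevalence of this profile, so no count or range is offered. Primary and secondary efficacy analyses, estimands and sample size are unaffected. The point should be corrected, because following one of the two passages to the letter leaves untested a group that the other requires to be tested.

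**What to change.** Reconcile Table 8-9, Table 8-1 footnote 14 and exclusion criterion 23 to a single serological definition that states explicitly whether the antigen or the antibody is meant, and use the same marker name in all three. Criterion 23 should also say plainly whether its parenthesis is the only route of entry for anti-HBc-positive participants. Then check the laboratory manual and the central laboratory's reflex testing against the agreed definition. The sponsor's medical team must decide which definition applies; this review does not.

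The drafting cost is small: a few lines in a protocol amendment and a check of the manual. Because an eligibility criterion is involved, the amendment needs ethics committee approval and, where required, health authority approval under Section 14.1. Enrollment was under way at Amendment 1, with 123 participants randomized, so the sponsor should also review which anti-HBc-positive participants have actually been tested.

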8.4.2 Electrocardiogram (ECG)

Electrocardiograms (ECGs) must be recorded according to the ECG investigator manual. The preferred sequence of cardiovascular data collection during study visits is ECG collection first, followed by vital signs, and blood sampling. The Fridericia QT correction formula (QTcF) should be used for clinical decisions.

Triplicate 12-lead ECGs are to be collected approximately 2 minutes apart for central analysis with ECG machines supplied by the core laboratory. The mean QTcF value for each visit will be calculated from the triplicate ECGs for each participant. At weeks 2, 12 and 52 pre and post-dose assessments should be collected (refer to [Table 8-1](#)), post dose assessment should be measured 

██████████ and the mean QTcF value for each timepoint will be calculated from the triplicate ECGs for each participant.

All ECGs, including unscheduled safety ECGs with clinically relevant findings collected during the study needs to be transmitted to the central ECG laboratory for review.

A monitoring or review process should be in place for clinically significant ECG findings throughout the study and especially at baseline before administration of study treatment.

In the event that a clinically significant ECG abnormality is identified at the site (e.g., severe arrhythmia, conduction abnormality of QTcF > 450 ms (males)/ 460 ms (females)), a copy of the assessment is sent to the core laboratory for expedited review if applicable, and the ECG is repeated to confirm the diagnosis. If the participant is hemodynamically compromised, the investigator or a medically qualified person must initiate appropriate safety procedures without delay (for example cardioversion).

Additional, unscheduled, safety ECGs may be repeated at the discretion of the investigator at any time during the study as clinically indicated. For any ECGs with participant safety concerns, two additional ECGs must be performed to confirm the safety finding.

Clinically significant abnormalities must be recorded on the CRF as either medical history/current medical conditions or adverse events as appropriate.

